5.2.7. Protocol deviations

Before database lock, all subject data on the CRF will be categorized according to the company's protocol deviation classification rules (critical, major, minor). All critical and major protocol deviations will be summarized and described by group and type, and a listing (including subject ID, protocol deviation reasons) will be provided for analysis.

5.3. Efficacy Analysis

The efficacy analysis will be performed based on the investigator's assessments. BOR, ORR, and CBR will be analyzed based on the FAS, PPS, and ES. DOR, TTR, 12-OS%, and OS will be analyzed based on the FAS. See [Table 1](#) for details. Efficacy should be presented by cohort/group.

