4.2 Blinding

This study is an open-label study and does not involve blinding.

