10 EFFICACY EVALUATION

The objective response rate (ORR), duration of response (DoR), clinical benefit rate (CBR), time to response, progression-free survival (PFS), 12-month survival, and overall survival (OS) will be evaluated.

The tumor imaging assessment will be performed once every 2 cycles (8 weeks) based on RECIST v1.1 (Appendix V). For subjects with CR/PR for the first time, the results should be confirmed after 4 weeks. The tumor assessment will be carried out once every 3 cycles (12 weeks) 6 months after the first dose of the drug.

Imaging results (including MRI and CT) of all subjects should be confirmed by blinded independent imaging experts. Subjects with efficacy evaluation results of CR, PR, SD, and PD should first be reviewed by the Principal Investigator (PI) of each study site, with all imaging results of response evaluation saved and finally collectively and independently assessed and confirmed by imaging experts.

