13 STATISTICAL ANALYSIS

13.1 Determination of Sample Size

The sample size in Stage I is primarily based on clinical considerations, and the number of subjects actually enrolled in each dose group is determined by the number of subjects who show clinically significant toxicity during the observation period for tolerability. During the expansion stage of PK study, 10-12 subjects are required for each group. The sample size in Stage I is 40-60 subjects.

In Stage II, for cohort 1, assuming that the ORR of the combination therapy is 30% with a bilateral alpha of 0.05, enrollment of 62 subjects will have a 80% power to ensure that the ORR of the combination therapy has a lower 95% CI limit of > 15%. If the dropout rate is 20%, 78 subjects should be enrolled.

For cohorts 2 and 3, assume that the ORR point estimate of each cohort is 30% and the width of the 90% confidence interval is 0.3, 38 subjects are required for each group when a 20% dropout rate is considered.

For cohort 4, assume that the ORR point estimate is 50% and the width of the 90% confidence interval is 0.4, 20 subjects are required to be enrolled.

In Stage II, the four cohorts require to enroll a total of 174 subjects.

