13.2 Statistical Hypotheses

The primary endpoint in Stage II is ORR.

Null hypothesis: $ORR = 15\%$

Alternative hypothesis: $ORR \neq 15\%$

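### The SAP bases the primary ORR and the other imaging endpoints on investigator readings and gives no role to the blinded independent confirmation that the protocol requires

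*SAP*

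**What the plan says.** Protocol section 10 states: "Imaging results (including MRI and CT) of all subjects should be confirmed by blinded independent imaging experts". It also sets an order. The site's principal investigator reviews CR, PR, SD and PD first, "with all imaging results of response evaluation saved and finally collectively and independently assessed and confirmed by imaging experts". The experts' assessment is therefore the last step.

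SAP 5.3 states: "The efficacy analysis will be performed based on the investigator's assessments". The SAP contains no ORR on the independent read, no sensitivity analysis and no concordance table. Its sections for other analyses (5.3.12 and 5.6) are marked not applicable, and it gives no reason for the choice of reader. SAP section 2 says that it was drafted from protocol version 5.0, so both texts are current.

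The sections that define and analyse ORR (protocol 13.4.3, SAP 4.1.1) do not name a reader. Protocol section 10 and SAP 5.3 therefore decide the point, and they conflict.

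Protocol 4.2 says "This study is an open-label study and does not involve blinding", and protocol 13.2 says "The primary endpoint in Stage II is ORR".

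**The concern.** Stage II has no concurrent control. Protocol 3.1 selects one dose level, and randomization under protocol 4.1 applies only if two doses are taken forward. Reader bias therefore has no comparator arm in which to cancel, and any net over-calling of response by investigators who know the treatment adds directly to the reported ORR.

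That ORR is read against a fixed figure. Protocol 13.2 puts the null at 15%, protocol 13.1 sizes cohort 1 so that the lower confidence limit clears 15%, and SAP 5.3.11 draws the ORR forest plots at 15% (30% for cohort 4). The protocol plans a safeguard for this setting, but the SAP gives it no place in the analysis.

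The endpoints exposed are those that depend on reading images: BOR, ORR, CBR, DoR, TTR, PFS and change in tumor size.

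**Working it through.** **Inputs.** Protocol 13.1, cohort 1: assumed ORR 30%, two-sided alpha 0.05, 62 subjects for 80% power; the criterion is that the ORR "has a lower 95% CI limit of > 15" percent; 20% dropout; 78 enrolled. Protocol 13.4.3 and SAP 5.3.2 specify a two-sided 95% Clopper-Pearson interval. The documents give no investigator-versus-independent discordance rate, so the net over-call *d* below is assumed.

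**Step 1: reproduce the plan's figure.** The lower limit for *x* responders of *n* is the 2.5% quantile of Beta(*x*, *n* − *x* + 1). At n=62:
- 15/62 = 24.2%, lower limit 14.2%: not above 15%.
- 16/62 = 25.8%, lower limit 15.5%: above 15%.

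The bar is therefore at least 16 responders. The exact binomial gives P(X ≥ 16 | 62, 0.30) = 80.3% and P(X ≥ 16 | 62, 0.15) = 1.9%. Dropout: 62/0.80 = 77.5, rounded up to 78. The plan's 62 and 78 reproduce. At n=78 the bar is 19 responders (lower limit 15.3%; 18/78 gives 14.3%).

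**Step 2: effect of an assumed over-call.** Take the independent ORR as 15%, so the investigator ORR is 0.15 + *d*. The chance of clearing the bar is P(X ≥ r | n, 0.15 + *d*), with r = 16 at n=62 and r = 19 at n=78.

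| Net over-call *d* | Investigator ORR | n=62, r=16 | n=78, r=19 |
|---|---|---|---|
| 0 | 15% | 1.9% | 2.0% |
| +1 point | 16% | 3.2% | 3.7% |
| +2 points | 17% | 5.2% | 6.2% |
| +3 points | 18% | 8.0% | 9.7% |
| +5 points | 20% | 16.2% | 20.3% |

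The n=62 column is the design size. The n=78 column is closer to the full analysis set if enrollment meets its target, because SAP 5.1.1 includes every enrolled subject who was dosed. Both columns are for cohort 1 alone. SAP section 5 also forms a driver-gene-negative population from cohort 1, cohort 3 and Stage I subjects, to which these figures do not apply.

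**Step 3: how many readings decide the result.** At the bar, one net downgrade on independent review is enough: 16/62 becomes 15/62, lower limit 14.2%. From about the assumed rate, 19/62 (30.6%, lower limit 19.6%), four net downgrades are needed. At n=78, from 23/78 (29.5%, lower limit 19.7%), five are needed: 18/78, lower limit 14.3%.

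**The case against.** Five arguments can be made for the plan as it stands.

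- **The protocol wording is soft.** Section 10 says that results should be confirmed. It does not say that the independent read is the primary analysis dataset, and it has no rule for disagreements. This stands in part: the documents do not settle which read was meant to be primary. But the requirement covers all subjects and places the experts last, so an analysis that ignores their reading does not match it.
- **Responses are confirmed after 4 weeks (SAP 4.1.1, 4.1.2).** The protocol's RECIST appendix (4.6.1) links the greater importance of central review to trials that drop confirmation, and this trial keeps it. That is a real mitigation of measurement error. It does not remove bias when the same unblinded reader makes both assessments.
- **SAP section 3 disclaims hypotheses and inference.** This stands as a limit on interpretation. A reader might take the table's percentages as error rates of a test in the SAP; the SAP performs none. They describe how often the protocol's 15% criterion would be met. The point estimate would be biased with or without a test.
- **Nothing shows that over-calling occurs.** Correct. A reader might infer that the investigator ORR is known to be inflated, or that the independent reading has been cancelled. The documents support neither: the reading can still take place under protocol section 10, and what is missing is its use in the analysis.
- **SAP 5.3 speaks of efficacy as a whole.** A reader might infer that every efficacy endpoint is compromised. OS and 12-month survival do not depend on image reading.

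**Conclusion.** The conflict between protocol section 10 and SAP 5.3 is real, is in current text, and concerns who determines the primary endpoint. Confidence in that is high.

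The size of any bias is unknown. The range of 1.9% to 16.2% (n=62) or 2.0% to 20.3% (n=78) assumes an independent ORR of exactly 15% in cohort 1 and a net over-call of 0 to 5 points. Over-calling from a true rate already above 15% would still overstate the ORR, but clearing 15% would not then be a false success.

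The sample-size arithmetic is sound and is not in question.

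**What to change.** **Preferred.** In SAP 5.3, base the primary ORR and BOR on the independent assessment that protocol section 10 already requires. Report the investigator-based results and a BOR concordance table as supportive. Report DoR, TTR, CBR and PFS on both reads. PFS and DoR should not simply move to the independent read: a subject may stop treatment on investigator-read PD before the experts would call PD, and that case needs its own rule.

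**Minimum.** If the investigator read stays primary, amend protocol section 10, justify the choice, and prespecify the independent-read ORR as a sensitivity analysis. Either change should be made before database lock, which is when SAP section 2 says that the plan is finalized.

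**Cost.** Transfer of the independent-read data, a second set of tables, and a stated rule for discordant reads, including whose PD date closes the ORR window in SAP 4.1.1. No new scan is needed, and N stays at 62/78. The headline ORR may be lower. The documents do not say which reader the assumed 30% refers to. If it is an investigator figure and the independent ORR is 27% or 25%, power on the independent read is 63.1% or 49.0% at n=62, and 73.9% or 59.5% at n=78.

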5.3.1. Best overall response (BOR)

See Section 4.1.2 for BOR.

BOR (CR, PR, SD, PD, and NE) will be summarized by frequency and percentage.

5.3.2. Objective response rate (ORR)

ORR is defined in Section 4.1.1.

ORR and its two-sided 95% CI will be calculated, the CI will be estimated using the Clopper-Pearson method, and a swimmer plot will be drawn.

5.3.3. Clinical benefit rate (CBR)

CBR is defined in Section 4.1.3.

CBR and its two-sided 95% CI will be calculated, and the CI will be estimated using the Clopper-Pearson method.

5.3.4. Duration of response (DoR)

DoR is defined in Section 4.1.4.

The Kaplan-Meier method will be used to analyze the median survival of DoR of each population/cohort, its 95% CI will be calculated using the Brookmeyer-Crowley method, and the DoR curve will be plotted. The Kaplan-Meier method will be used to analyze the 6-, 9-, and 12-month overall survival rates, and the corresponding two-sided 95% CIs will be calculated (using the log(-log) transformation by normal approximation with back transformation).

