5.3 Subject's Withdrawal

5.3.1 Criteria for withdrawal/treatment discontinuation

1. The subject withdraws informed consent and requests to withdraw from the study;
2. Imaging examinations show progressive disease;

Upon the first discovery of progressive disease by imaging examinations, it must be confirmed after 4 weeks (except for rapid progression and significant clinical progression);

If a subject shows local progression (1 to 4 lesions show progress) but the clinical symptoms are stable, the treatment can be continued according to the judgment of the investigator until imaging examinations show progressive disease again.

Definition of clinically stable: a. no clinically significant symptoms or changes in laboratory tests; b. no changes in the performance status score (deterioration); and c. non-tumor rapid progression and tumor progression not involving major organs/sites (e.g., spinal cord compression).

3. Treated by SHR-1210 for 2 years (no progressive disease as shown by imaging);
4. Subjects with intolerable toxicity;
5. Subjects with poor compliance;
6. Subjects lost to follow-ups or show positive blood HCG results;
7. Other reasons for which the investigator considers withdrawal as necessary.

Note: Subjects with radiologically confirmed PD may continue the study drug after providing informed consent for continuation after PD, if they are judged able to benefit from the study drug by the investigator. The treatment may continue until another radiographic PD or they can no longer benefit from the treatment. Subjects who continue the medication after PD will undergo periodic visits and efficacy evaluations according to the visit procedures specified in the protocol.

Subjects who agree to continue the treatment after PD should be fully informed of possible alternative treatments, potential risks of continuation, etc.

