4.2 Baseline Documentation of "Target" and "Non-target" Lesions

When more than one measurable lesion is present at baseline all lesions up to a maximum of five lesions total (and a maximum of two lesions per organ), representative of all involved organs should be identified as target lesions and will be recorded and measured at baseline (this means in instances where subjects have only one or two organ sites involved a maximum of two and four lesions respectively will be recorded).

Target lesions should be selected on the basis of their size (lesions with the longest diameter), be representative of all involved organs, but in addition should be those that lend themselves to reproducible repeated measurements. It may be the case that, on occasion, the largest lesion does not lend itself to reproducible measurement in which circumstance the next largest lesion which can be measured reproducibly should be selected.

Lymph nodes merit special mention since they are normal tissues which may be visible by imaging even if not involved by tumor metastasis. Pathological nodes which are defined as measurable and may be identified as target lesions must meet the criterion of a short axis of ≥ 15 mm by CT scan. Only the short axis of these nodes needs to be measured at baseline. The short axis of the node is the diameter normally used by radiologists to judge if a node is involved by tumor metastasis. Nodule size is normally reported as two dimensions in the plane in which

the image is obtained (for CT scan this is almost always the axial plane; for MRI the plane of acquisition may be axial, sagittal or coronal). The smallest of these measures is the short axis. For example, an abdominal node which is reported as being 20 mm × 30 mm has a short axis of 20 mm and qualifies as a malignant, measurable node. In this example, 20 mm should be recorded as the node measurement. Nodes with short axis ≥ 10 mm but < 15 mm should be considered non-target lesions. Nodes that have a short axis < 10 mm are considered non-pathological and should not be recorded or followed.

A sum of the diameters (longest for non-nodal lesions, short axis for nodal lesions) for all target lesions will be calculated and reported as the baseline sum diameters. If lymph nodes are to be included in the sum, then as noted above, only the short axis is added into the sum. The baseline sum diameters will be used as reference.

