4. STUDY ENDPOINTS

4.1. Efficacy Endpoints

4.1.1. Objective response rate (ORR)

ORR (according to RECIST v1.1) refers to the percentage of subjects with complete response or partial response (CR or PR), and subjects with first assessment as CR/PR should be reexamined 4 weeks later.

The ORR will be assessed based on the documented efficacy evaluation from the date of first dose to the date of disease progression (PD) or the start of new anti-tumor treatment, whichever occurs first. For subjects without PD or initiation of new anti-tumor treatment, ORR results will be assessed based on all efficacy evaluations.

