4.1.4. Duration of response (DOR)

Duration of response is defined as the time from the first documentation of CR or PR to the date of first documentation of PD or death.

The censoring rules are as follows:

- If there is no radiographic PD or death before the start of any new anti-tumor treatment, censoring will be based on the date of the last effective efficacy evaluation prior to the new anti-tumor treatment.
- If the subject does not have radiographic PD or die before the end of study or dropout, and has not received new anti-tumor treatment before the end of study or dropout, censoring will be based on the date of the last effective efficacy evaluation.
- For death or PD occurring after two or more missed planned visits, censoring will be performed based on the date of the last effective efficacy evaluation prior to death or PD.

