4.1.9. Change in tumor size (CTS)

The difference in tumor size from baseline as a percentage of baseline tumor size will be calculated based on the maximum decrease in tumor size or the minimum increase in tumor size after baseline.

Tumor size is defined as the sum of the longest diameters of target lesions assessed as per RECIST v1.1.

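### SAP 5.3.4 asks for overall survival rates where landmark DoR rates belong, and SAP 4.1.9 defines tumor size without the short-axis rule for nodes or an end of window; only the DoR landmarks and the waterfall plot are affected

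*SAP*

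**What the plan says.** **Duration of response.** SAP 4.1.4 defines DoR as "the time from the first documentation of CR or PR to the date of first documentation of PD or death", with its own censoring rules. SAP 5.3.4 begins on that quantity: "The Kaplan-Meier method will be used to analyze the median survival of DoR of each population/cohort". It adds a Brookmeyer-Crowley interval and a DoR curve. The next sentence changes endpoint: "The Kaplan-Meier method will be used to analyze the 6-, 9-, and 12-month overall survival rates", with log(-log) intervals.

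**Change in tumor size.** SAP 4.1.9 takes the largest decrease, or the smallest increase, at any point after baseline. It states: "Tumor size is defined as the sum of the longest diameters of target lesions assessed as per RECIST v1.1". Protocol Appendix V, section 4.2, builds the sum differently: "A sum of the diameters (longest for non-nodal lesions, short axis for nodal lesions) for all target lesions". The only planned output is a waterfall plot (SAP 5.3.9).

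**Assessment window.** ORR in SAP 4.1.1 uses evaluations "from the date of first dose to the date of disease progression (PD) or the start of new anti-tumor treatment", whichever is first, and BOR in 4.1.2 uses the same window. SAP 4.1.9 states no end. Protocol 5.3.1 allows treatment beyond progression and adds: "Subjects who continue the medication after PD will undergo periodic visits and efficacy evaluations".

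**The concern.** Three instructions, followed literally, give something other than what their section is for.

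1. OS is a different endpoint from DoR. It starts at first dose, and progression is not an event (SAP 4.1.8). OS rates do not say how long responses last. Durability matters here: DoR is a protocol secondary endpoint, and the rationale at the end of Protocol 1.7.2.4 gives sustained effect as one of two aims, alongside a higher short-term response rate.
2. The tumor-size definition cites RECIST 1.1 but contradicts its rule for nodal target lesions.
3. With no end of window, shrinkage seen after progression could count as a patient's best change, although it cannot count toward ORR or BOR.

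At stake are the landmark durability figures and the depth-of-response plot.

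**Working it through.** The plan states no figure for any of this, so there is nothing to reproduce. The check compares sections, followed by illustrations on assumed values.

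**Step 1: what the DoR landmarks should be.**

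| SAP section | Endpoint | Landmark months | Rate named |
|---|---|---|---|
| 5.3.4 | DoR | 6, 9, 12 | overall survival |
| 5.3.6 | PFS | 6, 9, 12 | PFS |
| 5.3.7 | 12-month OS | 12 | overall survival |
| 5.3.8 | OS | 12, 18, 24 | overall survival |

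The 5.3.4 grid and interval method match the PFS sentence, which names its own endpoint. The OS section uses another grid, and the 12-month OS rate already appears twice elsewhere. The likeliest explanation is a drafting slip for DoR rates. As written, no landmark DoR rate is specified.

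**Step 2: how far apart the two rates can be.** Assume exponential times, so the rate at month t is 0.5^(t / median), each endpoint on its own clock (DoR from first response, OS from first dose). The medians are assumptions. At 12 months:

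| Assumed DoR median | DoR rate | OS rate, median 12 | OS rate, median 18 | OS rate, median 24 |
|---|---|---|---|---|
| 6 | 25.0% | 50.0% (gap 25.0) | 63.0% (gap 38.0) | 70.7% (gap 45.7) |
| 9 | 39.7% | 50.0% (gap 10.3) | 63.0% (gap 23.3) | 70.7% (gap 31.0) |
| 12 | 50.0% | 50.0% (gap 0) | 63.0% (gap 13.0) | 70.7% (gap 20.7) |

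For example, 0.5^(12/6) = 0.250 and 0.5^(12/24) = 0.707. Under this model the rates agree only when the medians are equal.

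**Step 3: nodal target lesions.** Appendix V 4.2 gives a 20 x 30 mm node, recorded as 20 mm. The follow-up sizes below are assumed.

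- Node shrinks to 9 x 25 mm: short axis (9 - 20)/20 = -55.0%; longest diameter (25 - 30)/30 = -16.7%.
- Same node plus a non-nodal lesion going from 40 to 30 mm: RECIST sum (9 + 30)/(20 + 40) - 1 = -35.0%; all-longest sum (25 + 30)/(30 + 40) - 1 = -21.4%. The two fall on opposite sides of the 30% line for PR.
- Node shrinks to 14 x 20 mm: short axis -30.0%; longest diameter -33.3%. The direction of the discrepancy is not fixed.

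**Step 4: window.** Take a patient with progression from a new lesion at the first 8-week scan who continues treatment under Protocol 5.3.1, and whose target lesions are 35% below baseline at a later scan (assumed). BOR stops at the 8-week scan and is PD. SAP 4.1.9, read literally, allows a -35% bar.

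**The case against.** **The DoR wording is only a slip.** The same paragraph speaks loosely of the median survival of DoR, and the grid points to DoR rates. The DoR curve and the swimmer plot (SAP 5.3.2) would show durability anyway. This stands as an account of how the wording arose. It does not remove the problem: a programmer who follows the sentence produces OS rates, and one who corrects it silently departs from the SAP.

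**The longest-diameter bar may be impossible to produce.** Appendix V 3.1.1 has only the short axis of nodes measured and followed. If sites comply, the nodal long axis is not in the data, and the recorded sum is already the RECIST one. This largely stands and lowers the likely practical effect. The definition still contradicts the criterion it cites and should not be left to the programmer.

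**Stronger readings a reader might infer, which the documents do not support:**

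- *That DoR as a whole is computed on the wrong quantity.* Its definition, censoring, median, interval and curve are all on DoR.
- *That 5.3.4 reports OS among responders, a selected-survivor figure.* It states no such restriction; SAP 4.1.8 counts OS from first dose, and Table 1 places it on the FAS.
- *That tumor-size change is specified to run past progression.* SAP 4.1.9 is silent on this; it does not instruct use of later scans.
- *That duration and depth of response will not match RECIST.* DoR starts and ends on documented response and on PD or death, and CR, PR, BOR and ORR do not use the tumor-size variable.

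**The consequence is modest.** Tumor-size change is not a protocol endpoint and is absent from SAP Table 1. Protocol 13.4.3 promises only descriptive analysis for secondary endpoints such as DoR, so landmark rates are an SAP addition. This stands and sets the scale of the point.

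**Conclusion.** The point holds in a limited form. SAP 5.3.4 names the wrong quantity for the DoR landmark rates, and none is planned elsewhere. SAP 4.1.9 contradicts Appendix V on nodal target lesions and lacks the cut-off that ORR and BOR have, although post-progression evaluations can exist.

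The effect is confined to the DoR landmark rates and a descriptive waterfall plot. The primary endpoint ORR, and BOR, CBR, PFS and the OS analyses in 5.3.7 and 5.3.8, are unaffected.

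The size is not fixed by the documents. The 0 to 46 point gap at 12 months rests on exponential times and chosen medians; the node and window examples rest on assumed follow-up measurements. They show that the wording can matter, not how much it will. It would be wrong to conclude that reported responses will necessarily look more durable, since that requires OS to be programmed literally and then read as DoR.

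**What to change.** **SAP 5.3.4:** replace the overall survival rates with DoR rates, meaning the Kaplan-Meier probability of remaining in response at 6, 9 and 12 months, under the event and censoring rules of 4.1.4. Keep the stated interval method.

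**SAP 4.1.9:** define tumor size as the RECIST 1.1 sum of diameters (longest for non-nodal, short axis for nodal target lesions). Take the best change from scans up to first PD or the start of new anti-tumor treatment, as in 4.1.1 and 4.1.2.

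**Cost:** a few sentences and the matching programming, before the SAP is finalized ahead of database lock. No new data. Some rates or bars may become less favourable; others, as with the first node example, more so. At the assumed 30% ORR, cohort 1 would have about 19 responders among 62 (0.30 x 62 = 18.6), so landmark DoR rates will be imprecise.

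**Limit:** the new window will not make every waterfall bar agree with confirmed response. A patient with a new lesion and shrinking targets at the same scan, or with an unconfirmed PR, can still show a PR-size bar. Marking BOR on each bar would make this visible.
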